Official title: A Randomized Trial Examining Plasma Exchange using the BD Catheter In an Outpatient Apheresis Unit (REPLACE)

NCT number: NCT04253756 IRB Approved date: 4/22/2020 A Randomized Trial Examining Plasma Exchange using the BD Catheter In an Outpatient AphCresis Unit (REPLACE)

PI: [name] [name], CMSRN, QIA

Faculty Sponsor: [name] MD

Co-Investigator: [name], RN

Research manager: [name] PhD

Date: 11/27/2019

Version: 1

Introduction and Purpose

Nurses and apheresis technicians caring for patients requiring therapeutic apheresis procedures (TAP) utilize a wide range of intravenous catheters to obtain the access required to perform their procedures(Kalantari, 2012), (Golestaneh & Mokrzycki, 2013). The standard of care for our facility is to use an 18-gauge apheresis needle (Medisystems®) for the access site and an 18-gauge autogard catheter for the return site. Unfortunately, there is minimal literature defining best practices for catheter size selection(Salazar et al., 2017). At UT Southwestern Medical Center, our goal is to provide peripheral therapy to reduce the need for central access, such as a medical ports or tunneled catheters(Spires et al., 2018). However, the requirement for an 18 gauge catheter for an adequate return site, at times, rules out the patient for peripheral therapy(Putensen, Leverett, Patel, & Rivera, 2017). This requires central venous access to be obtained, which can delay the start of the procedure.

The lack of scientific evidence to support the use of smaller peripheral return catheters has increased the use of implanted ports in our institution(Putensen et al., 2017). The objectives of our pilot study are patient-centered and include analyzing the safety of using smaller peripheral return catheters without increasing the risk of hemolysis.

Background and Significance

TAP treats a wide range of disease processes and, in all cases, requires inlet and return venous access to perform the procedure. The goal of TAP is to return the patient to baseline and maintain independence and function. A larger needle (18 gauge) can cause more discomfort to the patient as well as additional scarring. A smaller needle may present less discomfort and scarring to the patient. Our goal in our outpatient clinic is to minimize disruption to the patient's routine and help them maintain normal activities of daily living.

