To accomplish these goals, our outpatient clinic is open Monday thru Friday offering 4 different appointment times. All patients that are referred to our clinic for TAP, first receive a vein evaluation to see if the patient is a candidate for peripheral IV therapy. At our clinic, approximately 68% of our TAP's are performed peripherally. This eliminates the risk of a central line infection and any alteration in activities of daily living, such as bathing(Kramer, 2016), (Shang, Ma, Poghosyan, Dowding, & Stone, 2014),(Keller et al., 2018; McDiarmid, 2015).

Our hypothesis, is that the 20-gauge BD Nexiva Diffusics catheter provides the same efficacy as current practice with no increase in adverse events for patients undergoing therapeutic apheresis. The results from our study will be significant because if the 20 guage needle is equally effective for TAP, it can increase the number of patients that would be candidates for peripheral therapy. Therefore, decreasing the need for central venous access, which place the patient at an increased risk of infection. Our study is a comparison of 2 types of infusion catheters. The standard of care is an 18-gauge autogard catheter (control group) which will be compared to the 20-gauge BD Nexiva Diffusics (intervention).

- P patients who require therapeutic apheresis procedures (TAP)
- I use of 20G BD diffusics catheter during apheresis
- C use of 18 G standard of care IV catheter during apheresis
- O no difference in efficacy and no increase in safety events

Concise Summary of Project

This is a randomized pilot study of TAP using the current standard of care catheter (SOC) vs the BD Nexiva Diffusics Catheter. It is a single blinded, randomized study. Data will be used to refine and power a full randomized control trial. For this study, a sample of 33 encounters in each group (total of 66 encounters). Our specific aim is to test the hypothesis that the 20-gauge BD Nexiva Diffusics Catheter provides the same efficacy and lower pain level with no increase in adverse events for patients undergoing apheresis treatments.

Randomization Procedure

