Measures of Quality of Apheresis will include inlet rate, and return pressures, procedure time. These measures are all readily available in the electronic medical record (EMR) and are all currently recorded as standard of care. The inlet rate is defined as the percent of patient inlet rate divided by the maximum allowable inlet rate. Because inlet rates are different for each type of TAP has a different maximum inlet rate, this will allow standardization across procedures. The max inlet rate for Photopheresis is 50ml/sec, the max inlet for plasma exchange is 100ml/sec inlet for red blood cell exchange is 55ml/sec. In addition, the inlet rate for each participant in the intervention arm will be compared to the average of their last 5 procedures. This measure will compare the efficiency of the SOC verses the intervention.

Inclusion Criteria

- Adult (≥ 18 years old)
- Speaks and reads English
- A patient of the Apheresis clinic at UT Southwestern University Hospital and Clinics
- Scheduled to receive TAP (therapeutic plasma exchange, red blood cell exchange and extracorporeal Photopheresis) as standard of care

Exclusion Criteria

- Prisoners
- Persons under the age of 18 years
- Patient who are actively involved in chemotherapy

Sources of Research Material

There are three sources of data for this study: electronic medical record (EMR) and paper-and-pen data collection from the patient's bedside (Data Collection form), and lab results provided by the UTSW laboratory via EMR. The EMR data that will be collected will include demographic information such as: age, sex, race, ethnicity, and admission diagnosis. The paper-and pen-data collection will include the patient self-reported pain level (VAS Scale), CBC collection, procedure data (minutes, inlet rate, return line pressures and alarms) total procedure time and post procedure sample. The paper-and-pen data collection form (Appendix 1) will record data only during patients TAP's encounter. Blood sample will be obtained from a SOC line. An additional 8 ml's for blood will be drawn from the patients for research purposes. Results from the bloodwork will be provided by the UTSW laboratory via the patient's EMR.

Recruitment Methods and Consenting Process

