For this study, patients will be recruited from the Apheresis Unit at UT Southwestern University Hospital and Clinics by a member of the research team. A member of the research team will screen the electronic medical record to determine a patient's eligibility. If a patient appears eligible for the study a member of the research team will discuss eligibility criteria with a member of the clinical team (nurse manger, nurse, physician, resident, fellow, social worker). The researcher will communicate with the clinical team to ensure eligibility: adult (≥18 years old), speaks and reads English, admitted to the Apheresis Unit at UT Southwestern University Hospital and Clinics at the time of consent. All patients in this study will be able to provide selfconsent (read and speak English).

When a patient is deemed eligible, a member of the research team will discuss consent and study procedures with that patient, in a place that is comfortable for the patient. After being approached by a member of the research team, patients will have up to next visit to consider participation in the study. The study team expects recruitment of 30 participants to last approximately 8 months. (Table 1)

Potential Benefits

There may or may not be a direct benefit to the participants in this study. Any additional blood test result that seems out of the norm will be shared with the nurse on duty or treating physician. We would also hope to share this with the greater research and clinical community in hopes of finding an alternative way for apheresis patients to have therapeutic apheresis procedures with less pain and no increase in adverse events.

Potential Risks

Risks associated with BD Cather:

Longer procedure time might occur if the inlet rate of the treatment is slower. The patient will be informed of this during the ICF process. With smaller catheters there's a risk of not obtaining the appropriate return rate for the patient. When the return rate is out of the SOC parameters the SOC apheresis equipment (Optia or Cellex) will alarm. If the alarm sounds 3 times the RN will decrease inlet rate by 5 ml/sec until the minimum threshold is reached (if needed), which is 50 ml/sec for plasma exchange and 35 ml/sec for RBC exchange and 20 ml/sec for photopheresis. If the alarm continues to when the minimum threshold is reached the catheter will

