efficacy wherein efficacy is represented by 1) the plasma hemoglobin value, and 2) the amount of time (minutes) required to complete a TAP. Hence models will be constructed to compare the mean plasma hemoglobin values by group, and to compare the mean number of minutes to complete TAP by group. Second, ANOVA will be used to compare the mean number of adverse events subjects experience in each group (intervention vs control).

Finally, a planned secondary analysis is to examine if the percent of lumen occupied by the return catheter is associated with return pressures. The suggested standard is that a catheter occupies < 45% of the inner-lumen diameter (measured with ultrasound). Return pressures >400 mm Hg are considered problematic. Chi-square analysis will be used to explore the odds of experiencing a return pressure > 400 mm Hg when the return catheter occupies <45% of the inner-lumen diameter.

Item	Month 1-2	Month 3-6	Month 4-8	Month 9-11	Month 12-18
IRB approval	Х				
Consent/	Х	X			
Enrollment					
Randomization	Х	X	Х	Х	
Data collection	Х	Х	Х	Х	
Manuscript				Х	X
prep					
Study closeout					X

Project Timeline

Enrollment of first patient (month 1), enrollment of the last patient (month 12), completion of data analysis (month 14), and manuscript submission (month 18). The apheresis team see approximatley 3000 TAP treaments each year. Of these, approximately 1500 encounters will meet the primary inclusion criteria. We anticipate that it will take less than 1-year to complete the study.

Future directions

The intention of this pilot study is to test the 20-gauge BD Nexiva Diffusics Catheter performance and efficacy. The findings from this study will be used to provide additional preliminary data to BD to support a National Institutes of Health or Agency for Healthcare Research and Quality (AHRQ) application (pending 2017 AHRQ funding announcements). Stakeholder feedback will be provided through an optional de-identified report to all patients and families.

Presentation of data

It is anticipated that the results from this study will be presented to American Society for Apheresis at their annual convention. The results will also be summarized in a manuscript and submitted for peer-review publication to Journal of Clinical Apheresis.

Appendix 1

Patient Sticker

A Randomized Trial Examining Plasma Exchange using the BD Catheter In an Outpatient Apheresis Unit The "REPLACE" study

Date SID Procedure Type						

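### Minutes are compared by catheter alone, pooled over three procedures with different maximum inlet rates, so a delay concentrated in plasma exchange could be averaged away

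*Combined protocol and SAP*

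**What the plan says.** Under Inclusion Criteria the trial takes any patient "Scheduled to receive TAP (therapeutic plasma exchange, red blood cell exchange and extracorporeal Photopheresis) as standard of care". The title names plasma exchange only.

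In the Statistical Analysis Plan, "efficacy is represented by 1) the plasma hemoglobin value, and 2) the amount of time (minutes) required to complete a TAP". For time, the model is "to compare the mean number of minutes to complete TAP by group". No procedure term, catheter-by-procedure term or per-procedure estimate is stated, and no equivalence or non-inferiority margin is given.

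Elsewhere the protocol recognises that the procedures differ. The paragraph on quality of apheresis, under Study procedure, states: "The max inlet rate for Photopheresis is 50ml/sec, the max inlet for plasma exchange is 100ml/sec inlet for red blood cell exchange is 55ml/sec". For that reason it expresses inlet rate as a percentage of the procedure's maximum. The minutes outcome gets no such treatment.

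Potential Risks links catheter to time: "Longer procedure time might occur if the inlet rate of the treatment is slower". After repeated alarms the inlet rate is stepped down to a minimum, "which is 50 ml/sec for plasma exchange and 35 ml/sec for RBC exchange and 20 ml/sec for photopheresis", before the catheter is replaced.

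Randomization Procedure describes a single list of 66 envelopes, not stratified by procedure. The form in Appendix 1 has a field for procedure type.

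**The concern.** A single mean difference over all encounters summarises the catheter effect well if that effect is similar in the three procedures. The stated rates give a reason to check this. The lowest rate allowed for plasma exchange (50) equals the highest for photopheresis (50) and is 91% of the highest for red cell exchange (50/55). A smaller catheter could therefore restrict plasma exchange while leaving the other two at full speed.

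In that case the pooled difference shrinks in proportion to the share of plasma-exchange encounters, which the plan neither fixes nor undertakes to report by arm. With no margin stated, a non-significant ANOVA could be taken as support for the same-efficacy hypothesis for TAP in general, including the procedure in the title. The pilot is also meant to inform the design and power of a full trial, and a diluted difference would carry over into that calculation.

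**Working it through.** **The plan's own figure.** The plan states 33 encounters per group but no alpha, power, SD, effect size or margin, so 33 cannot be reproduced. Several sets of inputs fit, for example a difference of 0.7 SD at two-sided 5% and 80% power. With 33 per group the difference detectable at 80% power is (1.96 + 0.84) × √(2/33) = 0.69 SD.

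**Step 1: can a flow limit fall unevenly?** Inputs are the stated maxima 100, 55 and 50. Assume a fixed volume, and an 18G catheter running at the maximum. Then time ratio = max(1, maximum rate / sustainable 20G rate).

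| Sustainable 20G rate (assumed) | Plasma exchange | Red cell exchange | Photopheresis |
|---|---|---|---|
| 80 | 1.25 | 1.00 | 1.00 |
| 60 | 1.67 | 1.00 | 1.00 |
| 55 | 1.82 | 1.00 | 1.00 |
| 50 | 2.00 | 1.10 | 1.00 |

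Any limit from 55 to just under 100 slows plasma exchange alone. Such a limit lies above the plasma-exchange minimum of 50, so the replacement rule would not be reached and the delay would stay in the 20G data.

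**Step 2: dilution.** If only plasma exchange is delayed, by D minutes, and it makes up a share w of encounters, the expected pooled difference is w × D. For the pooled test to reach 80% power, the plasma-exchange effect must be at least 0.69/w: 2.07 SD at w = 1/3, 1.38 at 1/2 and 1.03 at 2/3, before any variation between procedures is added.

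**Step 3: power.** Assumptions, none of them in the documents: two-sided 5%, 66 independent encounters, within-procedure SD 25 minutes, D = 30 in plasma exchange only, the remaining encounters split evenly between the other two procedures. Mean times for plasma exchange, red cell exchange and photopheresis are either all 120 minutes or 120/90/150.

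By hand at w = 1/3 with equal means:
- pooled difference = 30/3 = 10
- control-arm variance = 25² = 625
- 20G-arm variance = 625 + (1/3)(2/3)(30²) = 825
- standard error = √((625 + 825)/33) = 6.63
- power ≈ Φ(10/6.63 − 1.96) = Φ(−0.45) ≈ 0.33

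With means 120/90/150 the variances are 625 + 600 = 1225 and 625 + 800 = 1425. The standard error is 8.96 and power ≈ Φ(10/8.96 − 1.96) ≈ 0.20. Simulation with 4000 runs per setting agrees; the ranges below span the two sets of means and simulation error.

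| Plasma-exchange share | Pooled difference (min) | Planned ANOVA | Procedure main effect added | Plasma-exchange contrast |
|---|---|---|---|---|
| 20% (13 encounters) | about 6 | 10-15% | 13-14% | about 54% |
| 1/3 (22) | about 10 | 20-31% | 32-33% | 77-79% |
| 1/2 (33) | about 15 | 41-60% | 63-65% | 91-92% |
| 2/3 (44) | about 20 | 71-85% | 88-89% | 97-98% |

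A procedure main effect removes between-procedure noise but still returns one averaged catheter effect. Only the catheter-by-procedure term shows where a delay sits.

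**Step 4: the opposite scenario.** If the delay is 20 minutes in every procedure, the planned ANOVA has 57-90% power with 13 to 22 plasma-exchange encounters, and the model with a procedure main effect about 88%. The plasma-exchange contrast has only 27-46%.

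**The case against.** The strongest reply is that the pooled difference answers the question the plan asks. The hypothesis and the eligibility criteria concern TAP as a whole, and only the title singles out plasma exchange. This stands. A reader might infer that the plan will declare same efficacy specifically for plasma exchange, but no such conclusion is planned. The risk lies in how an overall statement would be read.

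A reader might also infer that the 20G is expected to fail only at plasma-exchange flow and that the other encounters cannot show a delay. The documents do not support that. They give no flow limit for the 20G, and Potential Risks foresees step-downs in all three procedures. The time ratios are also favourable to the concern. The catheter under test is on the return line, whereas the ratios use inlet maxima, and they assume that the 18G runs at the maximum. If 18G plasma exchange ran at 75 (an assumption), a 20G limit of 60 would give 75/60 = 1.25, not 1.67.

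The mix is unknown, and dilution is modest if plasma exchange predominates. Step 4 adds that replacing the overall comparison with procedure-specific conclusions would lose power when the delay is common to all types.

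There is partial handling too. Inlet rate is standardised by procedure and, for the intervention arm, compared with each patient's last 5 procedures, and return pressures and alarms are recorded every 15 minutes. But the Statistical Analysis Plan does not carry inlet rate into its efficacy models, and a pooled percentage would be diluted in the same way. Pilot status limits what 66 encounters can prove; it does not remove the value of a by-procedure table.

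**Conclusion.** The concern holds in conditional form. The efficacy model for minutes ignores a difference between procedures that the protocol acknowledges elsewhere, and an uneven catheter effect would go unseen. Under the Step 3 assumptions the planned ANOVA would miss a 30-minute plasma-exchange delay in about 85-90% of trials at a 20% share (100 minus 10-15) and 69-80% at one-third, but only 15-29% at two-thirds. Mix, SD and delay are all assumed. Encounters were treated as independent although one patient may contribute up to 10, so the power figures may be optimistic.

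The documents do not show that the 20G slows plasma exchange, nor that the pooled analysis is wrong for a hypothesis about TAP. They also do not justify resting every efficacy statement on a procedure-specific estimate. The calculation concerns minutes; no corresponding check was made for plasma hemoglobin. The false-reassurance risk comes partly from the absence of a margin, which is a separate gap that this point does not close. Confidence is medium; the change is worth making because it is cheap.

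**What to change.** In the Statistical Analysis Plan:

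1. Add procedure type to the model for minutes and keep the procedure-adjusted overall catheter difference as the main estimate.
2. Fit a second model with catheter-by-procedure-type. For each of the three procedures, report the 20G-minus-18G difference in minutes with a 95% CI and the number of encounters by arm. Do the same for percent inlet rate.
3. State that any overall same-efficacy conclusion will be qualified if the per-procedure estimates diverge, or if the interval for a procedure, plasma exchange in particular, still includes a material delay.

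The cost is a few lines of text and one table, since procedure type is already on the data collection form. The downside is wide per-procedure intervals, wider still once repeat encounters in the same patient are allowed for, and possibly nothing useful to say about a rare type. The per-procedure results should be presented as estimation and not as three separate tests.

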After an eligible participant is consented to the study the patient will be randomized without replacement to the use of one of the two catheters. Using a random number generator, numbers between (1-66) were randomly divided into two groups: SOC Control group and BD Intervention group (Figure 1). A study identification number (SID) key will be saved on a UTSW approved secure device and only the research coordinator will have access to the SID key showing which SID coordinates with each group. This will ensure that unblinding can occur is necessary and there is a backup to randomization.

The research coordinator will have 66 randomized envelops without replacement. Half of the envelops will be assigned to 18G catheter SOC (control) and the other half be assigned to

20G BD Nexiva Diffusics catheter (intervention). The PI will be blinded, therefore the PI will pick an envelope when patients are consented and ready for treatment. Participants will be randomized after they have consented to the study. Participants' will then be randomized to one of the two groups again at each encounter (i.e., SOC visit). Inside the envelope it will tell the investigator if the patient is in the control or intervention group of the study.

To promote a more representative sample, each patient may participate a maximum of 10 times.

Study procedure:

[figure not shown]
Each enrolled patient will participate in the study will be randomized at each encounter. During each encounter the following information will be captured:

- 1. CBC
- 2. Patient discomfort

level with placement of catheter

- 3. Inlet rate
- 4. Return line pressures
- 5. Procedures alarms
- 6. Procedure total time
- 7. Post procedure sample

Treating nurse (RN) will start the TAPs procedure with one of the 2 catheters. During the intervention period, the RN will be at bedside during as it is SOC in the Apheresis unit however for the purpose of this study the RN will have the study data collection form (DCF, Appendix1). The RN will complete the pre-assessment including a pain assessment to establish pain level prior to procedure that is currently documented in the electronic medical record. The patient will be asked to self-report the pain level after the return line has been started on the visual analog scale (VAS) Scale from 0mm to 100mm "0 being the lowest/ no pain, 100mm being the highest

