be replaced with the SOC 18-gauge catheter. Obtaining blood samples may cause some discomfort, feeling lightheaded, fainting, bruising, clotting, and bleeding from the site of the needle stick and, in rare cases, infection. The risks are mitigated by drawing blood from a line that has already been established as part of SOC.

There is a low risk of breach in confidentiality. Subjects will be assigned individual study identification (SID) numbers and no personal identifiers will be included in the final summary.

Patients who are randomized to the 20-guage needle group and who fail the intervention will be given the 18-guage standard of care needle. At the patient's next visit, the patient will once again be randomized. If the patient is randomized into the 20-guage needle arm and fails the intervention a second time, the patient will be removed from the study.

Procedures to Maintain Confidentiality

Study participants will be given a study identification (SID) number. Only the approved study personnel and the principal investigator have access to the database linking the SID to the patient name. This database is kept on a protected drive on a password protected computer. Paper or hard copy participant records will be kept in a locked file cabinet in a locked office. If any identifying information is transmitted, it will be done so via secure e-mail and/or dedicated fax machines.

Statistical Analysis Plan

All data will be first collected on the DCF (Appendix I) and then entered into an electronic spreadsheet (e.g., MS Excel) which will be converted to SAS v 9.4 for analysis. All statistical analyses will be performed at UTSW in a location with secure data encryption capability. Initially, the data will be summarized first using standard measures of central tendency (mean, median, standard deviation, and interquartile range) for each variable. These will be examined to support the assumption of being approximately normally distributed. Baseline characteristics will be summarized using appropriate parametric and non-parametric measures.

The primary hypothesis is that the 20-gauge BD Nexiva Diffusics catheter provides the same efficacy of current practice with no increase in adverse events for patients undergoing therapeutic apheresis. This will be examined in 2 steps. First, ANOVA will be used to explore

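### The by-group comparison of procedure minutes ignores each patient's pre-study procedure times, which the EMR holds: a modest, cheaply recovered loss of precision

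*Combined protocol and SAP*

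**What the plan says.** The Statistical Analysis Plan opens the primary analysis with "First, ANOVA will be used to explore" efficacy, represented by plasma hemoglobin and by minutes to complete a procedure. For the latter, the model will "compare the mean number of minutes to complete TAP by group". No covariate, procedure type or patient effect is named.

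The Study procedure section states "Measures of Quality of Apheresis will include inlet rate, and return pressures, procedure time", and says of them: "These measures are all readily available in the electronic medical record (EMR) and are all currently recorded as standard of care". It goes on to plan that "the inlet rate for each participant in the intervention arm will be compared to the average of their last 5 procedures". Nothing in the plan uses earlier procedure times for the minutes outcome.

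On design, the Concise Summary of Project sets 33 encounters per group, 66 in all, and calls the study a pilot. Under Randomization Procedure, participants are "randomized to one of the two groups again at each encounter", and "each patient may participate a maximum of 10 times". The recruitment section expects 30 participants. Three procedure types are pooled (Inclusion Criteria). Inlet rate is standardised across types; minutes are not.

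**The concern.** A pre-study value of a primary outcome is said to be on record, and the plan already intends to open patients' earlier procedures for another measure. Without it, stable differences between patients in procedure duration stay in the error term. The number of encounters is fixed, so any extra precision has to come from the analysis. The primary hypothesis is that efficacy is the same, and a wide interval supports a sameness claim poorly. The pilot is also meant to inform a full trial, for which the correlation between earlier and current minutes would be useful.

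**Working it through.** **Inputs.** From the documents: 33 encounters per arm, 30 expected patients (66/30 = 2.2 encounters each), at most 10 encounters per patient, a 5-procedure look-back. Assumed, because the documents give none: two-sided 5% level, a true difference of 0.5 SD, the correlation rho between earlier and current minutes, and the share of variance lying between patients (ICC).

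**The plan's own figure.** The 33 per group comes with no power, SD or effect size, so it cannot be reproduced. For reference, the difference detectable with 80% power is (1.96 + 0.842) × √(2/33) = 0.69 SD.

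**Step 1: against plain ANOVA.** A covariate correlated rho with the outcome multiplies the residual SD by √(1 − rho²). The noncentrality is 0.5/√(1 − rho²) × √(33/2).

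| rho | Residual SD | Noncentrality | Power |
|---|---|---|---|
| 0 | 1.000 | 2.03 | 52% |
| 0.3 | 0.954 | 2.13 | 55% |
| 0.5 | 0.866 | 2.35 | 64% |
| 0.65 | 0.760 | 2.67 | 75% |

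The interval narrows in proportion to the residual SD: by about 5%, 13% and 24%.

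**Step 2: what rho a 5-procedure mean could give.** rho = ICC/√(ICC + (1 − ICC)/5), which is 0.33, 0.45 and 0.65 at ICC 0.2, 0.3 and 0.5.

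**Step 3: gain beyond a patient term.** The variance of the group effect was computed by generalised least squares for 24 patients with 2 encounters and 6 with 3 (48 + 18 = 66), averaged over 400 random 33:33 allocations. At ICC 0.5 it is 0.0606 for ANOVA, 0.0441 with a random patient effect, and 0.0344 with the prior mean added. The 95% half-widths, 1.96 × √variance, are 0.48, 0.41 and 0.36 SD. Normal-approximation power is 53%, 66% and 77%. At ICC 0.3 the prior mean takes power from 57% to 63%; at ICC 0.2, from 55% to 58%. A separate simulation (30 patients, 1,500 runs per setting) gave 58% to 62% at ICC 0.3 and 68% to 75% at ICC 0.5, with type I error near 5%.

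**Step 4: gain beyond patient and procedure-type terms (30 patients).** Some between-patient variance may simply be procedure type. The share is assumed.

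| Type's share of between-patient variance | ICC 0.2 | ICC 0.3 | ICC 0.5 |
|---|---|---|---|
| None | about 3 points | about 6 points | about 10 points |
| Half | 57% to 58% | 60% to 63% | 70% to 76% |
| Three-quarters | under 1 point | about 1 point | about 3 points |

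For the 70% to 76% cell, 0.5/SE = 1.96 + 0.524 = 2.484 becomes 1.96 + 0.706 = 2.666, so the interval is 1 − 2.484/2.666 = about 7% narrower.

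**Step 5: fewer patients with more encounters each.** At ICC 0.5, a patient term alone gives about 76% with 12 patients, and adding the prior mean gives 79%. With 7 patients it is 78–79% against 80%. The simulation with 12 patients gave 74% to 78%, where each figure has a Monte Carlo error of about √(0.75 × 0.25/1500) = 1.1 points.

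**The case against.** The strongest reply is that the gain is credited to the wrong term. Procedure type is already on the data collection form (Appendix 1) and costs nothing to use, and a patient effect is natural when patients return. Steps 3 to 5 show that this largely stands: the 52% to 64% contrast is not the gain from pre-study minutes alone. The 30-patient layout may also be optimistic. Up to 10 encounters per patient are allowed, and the timeline table ends enrolment by month 6 while randomisation runs to month 11, which fits repeated visits (although the Project Timeline text puts the last enrolment at month 12).

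The history may also be incomplete or not comparable. Eligibility requires no earlier procedures. Only about 68% of the clinic's procedures are peripheral, so some earlier times may come from central access. Nothing shows that the EMR time is defined as on the study form. Each of these would lower the gain. If 30% of patients had no history (assumed), the 10-point gain at ICC 0.5 would fall to about 8.

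A reader might infer that the comparison is biased, or that the trial falls short of its intended power. The documents support neither. Omitting a prognostic covariate leaves the randomised contrast unbiased. The study is an exploratory pilot with no power target or margin, so there is no target to miss.

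What survives is the direction. Where earlier times exist and predict current ones, using them narrows the interval, and no other part of the plan does so.

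**Conclusion.** The point holds as a modest loss of efficiency. Beyond patient and type terms, with 30 patients, the prior mean is worth about 1 to 10 points of power at a 0.5 SD difference: about 6 at ICC 0.5 and 3 at ICC 0.3 if type explains half of the between-patient variance. With 7 to 12 patients it is worth about 1 to 3 points. Every figure rests on an assumed ICC or correlation, and on usable earlier procedure times for most patients. If that correlation is weak the gain is negligible.

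**What to change.** In the Statistical Analysis Plan, replace the by-group ANOVA of minutes with a mixed model containing group, procedure type, a random patient effect and the patient's pre-study mean minutes. Define that mean as follows:

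- up to 5 procedures of the same type, with peripheral access where the record shows it, all completed before the first study encounter, so that no study catheter can affect them;
- taken from the EMR in the same way for every participant, whatever the allocation;
- the available values when fewer than 5 exist;
- the overall mean plus a missing indicator when none exist, so that no encounter is dropped.

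Report the unadjusted difference alongside.

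The cost is SAP wording, about 150 EMR values (30 patients × 5), and one or two degrees of freedom for the prior mean and its indicator. Patients without history gain little. No extra patients or procedures are needed.
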